#### 5.0 Randomization

Participants will be randomized into FIT, CBT or GAE groups based upon a randomization schedule maintained by the study biostatistician. A randomization process *by group* will be used. In other words, after a sufficient number of approximately 4 to 6 patients have been screeened at a site and found to be eligible, the biostatistician will inform the therapist of the next group assignment. Randomization will be stratified by site in order to ensure approximately equal proportions of patients from each site in each of the 3 arms. Group assignments will be masked to the PI and study assessors. The study biostatistician ([name]) will monitor the equivalence of sample size in each treatment arm and at study mid-point will make any adjustments to the randomization schedule in consultation with the DSMB to ensure approximately equal group sizes by the end of the study.

# 6.0 Derivations and Definitions

## Variable Definitions

# Demographics and Study Status

Variable	Descriptor	Derivation (if applicable)
Site	Institution Name	
SiteID (derived)	Site ID Number	IF Site=Cincinnati Children's Hospital Medical Center, 10; IF Site= Children's Mercy Hospitals and Clinics, 30; IF Site=Connecticut Children's Medical Center, 40; IF Site= Nationwide Children's Hospital, 50; IF Site= The Hospital for Sick Children, 60; IF Site= Boston Children's Hospital, 70; IF Site= Indianapolis Riley Children's Hospital, 80
Subject	Study ID [2-digit site ID]-[3-digit subject ID]	
mGROUP	Masked Group Assignment (A, B, C)	(From Randomization Record) (mGROUP to be edited to GROUP after primarily analysis complete)
GROUP	Group Assignment (CBT, FIT, GAE)	(From Randomization Record)
FORMAT	Treatment Delivery Format (In-person=1, Remote=2)	(From Randomization Record)
COHORTID_STD	Cohort ID (01-18)	
RFENROLLDTE_R AW	Date of Enrollment (Signed Consent)	
BRTHDAT_RAW	Participant's date of birth	
SEX_STD	Participant's sex 1=male; 2=female; 99 = other	
RACE_STD	Participant's race	Variable Labels: 1=More than one race; 2=Caucasian/White; 3=African American/Black; 4=Asian; 5=Native Hawaiian/Other Pacific Islander; 6= American Indian/Alaskan Native
ETHNIC_STD	Participant's ethnicity	Variable Labels: 1=Hispanic; 2=Non-Hispanic
INCOME_STD	Family Income	Variable Labels: 1=Less than \$24,999; 2=\$25,000 - \$49,999;

Beschipton	Derivation (il applicable)
•	3=\$50,000 - \$74,999;
	4=\$75,000 - \$99,999;
	5=\$100,000 - \$124,999;
	6=\$125,000 - \$149,999;
	7=More than \$150,000;
	8=Prefer not to answer;
	99=Unknown
Insurance Status	Variable Labels:
	1=Private Health Insurance;
	2=Medicare; 3=Medicaid;
	4=Military Health Care; 5=State
	Specific; 6= Indian Health
	Services; 7=Non-Us; 8=Other; 9
	= None
Caregiver 1	Variable Labels:
	1=Mother; 2=Father; 3=Legal
	Guardian
Caregiver 1 level of education	Variable Labels:
	1=Less than High School;
	2=High School/GED; 3=Partial
	College or Trade School;
	4=College Graduate; 5=Post
O and altern O	Graduate Degree
Caregiver 2	Variable Labels:
	1=Molner; 2=Faller;
Coregiver 2 level of education	3=Legal Guardian
Caregiver 2 level of education	1-Loss than High School:
	2-High School/CED: 2-Dartial
	College or Trade School:
	A=College Graduate: 5=Post
	Graduate Degree
Participant's grade enrolled	Variable Labels
r a topanto grado chiolica	$1=5^{\text{th}}$ $2=6^{\text{th}}$ $3=7^{\text{th}}$ $4=8^{\text{th}}$ $5=9^{\text{th}}$
	$6=10^{\text{th}}$ $7=11^{\text{th}}$ $8=12^{\text{th}}$
	Insurance Status Caregiver 1 Caregiver 1 level of education Caregiver 2 Caregiver 2 level of education Participant's grade enrolled

## **Assessment Time Point**

Variable	Descriptor	Derivation
TIMEPOINT	Assessment Visit	IF FolderName=T1 - (Baseline);
	number	IF FolderName=T2 - (Tx Session 8 -
		Mid-Tx Check-In);
		IF FolderName=T3 - (Post-Tx
		Assessment);
		IF FolderName=T4 - (3-month
		Follow-Up);
		IF FolderName=T5 - (6-month
		Follow-Up);
		IF FolderName=T6 - (9-month
		Follow-Up);

IF FolderName=T7 - (12-month Follow-Up)

# **Derived Variable Definitions**

#### Demographics

Variable	Descriptor	Derivation (if applicable)
T1AGE	Participant age at enrollment in years	(RFENROLLDTE_RAW –
(derived)	NOTE: RFENROLLDTE is pulled from the	BIRTHDAT_RAW)/365.25
	Randomization Form (11 folder); BIRTHDAT is pulled	
	from the Demographics form (pre-screen folder)	

# Primary Outcome: Functional Disability T1-T7

Variable	Descriptor	Derivation (if applicable)
FDITOT	Functional Disability Inventory score	Σ(FDIBATH_STD,
(derived)		FDISTAIRS_STD,
		FDIFRIEND_STD,
		FDICHORES_STD,
		FDIEATING_STD, FDIREST_STD,
		FDIRIDING_STD,
		FDISCHOOL_STD,
		FDIACTIVITIES_STD,
		FDIHOMEWORK_STD,
		FDIWATCHING_STD,
		FDIWALK_STD, FDIRUN_STD,
		FDISHOP_STD, FDISLEEP_STD)

# Secondary Outcome: Pain Intensity Rating T1-T7

Variable	Descriptor	Derivation (if applicable)
PRFAVGPN_RAW	Average Pain Diary VAS rating	
FDIMPSCR_RAW	Retrospective Pain VAS Rating	

# Other Variables T1, T3-T7

Variable	Descriptor	Derivation (	if applicable)
CDITOT	Children's Depression Inventory 2	COMPUTE	CDI2ITEM1_STD =
(derived)	Raw score		CDI2ITEM1_STD -1.
(donvod)		COMPUTE	CDI2ITEM2_STD =
			CDI2ITEM2_STD -1.
		COMPUTE	CDI2ITEM3_STD =
			CDI2ITEM3_STD -1.
		COMPUTE	CDI2ITEM4_STD=
			CDI2ITEM4_STD -1.
		COMPUTE	CDI2ITEM5_STD=
			CDI2ITEM5_STD -1.
		COMPUTE	CDI2ITEM6_STD=
			CDI2ITEM6 STD -1.
		COMPUTE	CDI2ITEM7_STD=
			CDI2ITEM7_STD -1.

Variable	Descriptor	Derivation (in	f applicable)
		COMPUTE	CDI2ITEM8 STD=
			CDI2ITEM8 STD -1.
		COMPUTE	CDI2ITEM9 STD=
			CDI2ITEM9 STD -1.
		COMPUTE	CDI2ITEM10 STD=
			CDI2ITEM10_STD -1.
		COMPUTE	CDI2ITEM11_STD =
			CDI2ITEM11_STD -1.
		COMPUTE	CDI2ITEM12_STD =
			CDI2ITEM12_STD -1.
		COMPUTE	CDI2ITEM13_STD =
			CDI2ITEM13_STD -1.
		COMPUTE	CDI2ITEM14_STD =
			CDI2ITEM14_STD -1.
		COMPUTE	CDI2ITEM15_STD =
		COMPLITE	CDIZITEM15_STD -1.
		COMPUTE	CDI2ITEM16_STD -
		COMPLITE	CDI2ITEM17_STD -
			CDI2ITEM17_STD -1
		COMPLITE	CDI2ITEM18 STD =
			CDI2ITEM18 STD -1.
		COMPUTE	CDI2ITEM19 STD =
			CDI2ITEM19_STD -1.
		COMPUTE	CDI2ITEM20_STD =
			CDI2ITEM20_STD -1.
		COMPUTE	CDI2ITEM21_STD =
			CDI2ITEM21_STD -1.
		COMPUTE	CDI2ITEM22_STD =
			CDI2ITEM22_STD -1.
		COMPUTE	$CDI2ITEM23_STD = CDI2ITEM22_STD = 1$
		COMPLITE	
			CDI2ITEM24 STD =
		COMPUTE	CDI2ITEM25 STD =
			CDI2ITEM25 STD -1.
		COMPUTE	CDI2ITEM26 STD =
			CDI2ITEM26_STD -1.
		COMPUTE	CDI2ITEM27_STD =
			CDI2ITEM27_STD -1.
		COMPUTE	CDI2ITEM28_STD =
		EXECUTE	CDI2ITEM28_STD -1.
		RECODE CDI2I	TEM2_STD
		CDI2ITEM6_ST	D CDI2ITEM7_STD
			D CDIZITEMIU_STD
		CDI2ITEM24 S	TD CDI2ITEM26 STD
		CDI2ITEM27	STD (2=0) (1=1) (0=2).
		EXECUTE.	_ 、 , 、 , 、 ,
		COMPUTE CDI	sum =
		CDI2ITEM1 ST	D+CDI2ITEM2 STD+CDI2I
		TEM3 STD+CD	I2ITEM4_STD+CDI2ITEM5
		_STD+CDI2ITEI	M6_STD+CDI2ITEM7_STD
		+CDI2ITEM8_S	TD+CDI2ITEM9_STD+CDI2
		ITEM10_STD+C	DI2ITEM11_STD+CDI2ITE
		M12_STD+CDI2	2ITEM13_STD+CDI2ITEM1

Variable	Descriptor	Derivation (if applicable)
		4 STD+CDI2ITEM15 STD+CDI2ITEM16 S TD+CDI2ITEM17 STD+CDI2ITEM18 STD +CDI2ITEM19 STD+CDI2ITEM20 STD+C DI2ITEM21 STD+CDI2ITEM22 STD+CDI2I TEM23 STD+CDI2ITEM24 STD+CDI2ITE M25 STD+CDI2ITEM26 STD+CDI2ITEM2 7 STD+CDI2ITEM28 STD. EXECUTE.
PCSTOT (derived)	Pain Catastrophizing Scale score	Σ(PCS1_STD,,PCS13_STD)
PCQTOT (derived)	Pain Coping Efficacy score	RECODE PCQDEAL_STD (1=5) (2=4) (3=3) (4=2) (5=1) EXECUTE.
		COMPUTE PCQTOT = PCQCHANGE_STD + PCQDEAL + PCQMOOD_STD. EXECUTE.
TSKTOT (derived)	Tampa Scale of Kinesiophobia score	Σ(TSKHURT_STD,TSKPUSH_STD ,TSKWRONG_STD,TSKCONDITIO N_STD,TSKRISK_STD,TSKINJUR ED_STD,TSKCAREFUL_STD, TSKDANGEROUS_STD,TSKEXER CISE_STD, TSKNORMAL,TSKPAIN_STD)
PAININT (derived)	PROMIS Pain Interference	$\Sigma$ (PPISLEEP_STD, PPIANGRY_STD, PPISCHOOLWK_STD, PPIATTENTION_STD, PPIRUN_STD, PPIWALK_STD, PPIFUN_STD, PPISTAND_STD)
PAININTt (derived)	PROMIS Pain Interference t-score	IF PAININT = 8, 34.0 IF PAININT = 9, 38.7 IF PAININT = 10, 40.6 IF PAININT = 11, 42.7 IF PAININT = 12, 44.3 IF PAININT = 13, 45.8 IF PAININT = 14, 47.1 IF PAININT = 15, 48.4 IF PAININT = 16, 49.5 IF PAININT = 17, 50.6 IF PAININT = 18, 51.7 IF PAININT = 19, 52.7 IF PAININT = 20, 53.7 IF PAININT = 21, 54.7 IF PAININT = 22, 55.7

Variable	Descriptor	Derivation (if applicable)
	•	IF PAININT = 23, 56.6
		IF PAININT = 24, 57.6
		IF PAININT = 25, 58.5
		IF PAININT = 26, 59.5
		IF PAININT = 27, 60.4
		IF PAININT = 28, 61.4
		IF PAININT = 29, 62.4
		IF PAININT = 30, 63.4
		IF PAININT = 31, 64.4
		IF PAININT = 32, 65.4
		IF PAININT = 33, 66.5
		IF PAININT = 34, 67.6
		IF PAININT = 35, 68.8
		IF PAININT = 36, 70.1
		IF PAININI = $37, 71.5$
		IF PAININT = $38, 73.2$
		IF PAININT = $39, 75.0$
		IF PAININI = 40, 78.0
FATIG	PROMIS Fatique	$\Sigma$ (PFFRIENDS STD.
(derived)	5	PFWEAK STD. PFEASILY STD.
		PFSCHOOLWK STD,
		PFFINISHING STD,
		PFSTARTING STD,
		PFATTENTION STD,
		PFSPORTS_STD,
		PFTHINGS_STD, PFENJOY_STD)
FATIGt	PROMIS Fatigue t-score	IF FATIG = 10, 30,3
(derived)		IF FATIG = 11, 34.3
(		IF FATIG = 12, 36.9
		IF FATIG = 13, 39.0
		IF FATIG = 14, 40,9
		IF FATIG = 15, 42,5
		IF FATIG = 16, 44.0
		IF FATIG = 17, 45.4
		IF FATIG = 18, 46.7
		IF FATIG = 19, 47.9
		IF FATIG = 20, 49.1
		IF FATIG = 21, 50.2
		IF FATIG = 22, 51.3
		IF FATIG = 23, 52.4
		IF FATIG = 24, 53.5
		IF FATIG = 25, 54.5
		IF FATIG = 26, 55.6
		IF FATIG = 27, 56.6
		IF FATIG = 28, 57.6
		IF FATIG = 29, 58.6
		IF FATIG = 30, 59.6
		IF FATIG = 31, 60.6

Variable	Descriptor	Derivation (if applicable)
		IF FATIG = 32, 61.6 IF FATIG = 33, 62.6 IF FATIG = 34, 63.6 IF FATIG = 35, 64.6 IF FATIG = 36, 65.6 IF FATIG = 37, 66.7 IF FATIG = 39, 68.7 IF FATIG = 40, 69.8 IF FATIG = 41, 70.9 IF FATIG = 42, 72.0 IF FATIG = 43, 73.2 IF FATIG = 44, 74.4 IF FATIG = 45, 75.7 IF FATIG = 46, 77.0 IF FATIG = 47, 78.5 IF FATIG = 49, 82.0 IF FATIG = 50, 84.0
PAINBEH (derived)	PROMIS Pain Behavior	∑(PPBFACE_STD, PPBMEDICINE_STD, PPBTALKED_STD, PPBMOVED_STD, PPBPROTECTED_STD, PPBSTOP_STD, PPBHELP_STD, PPBLAYDOWN_STD)
PAINBEHt (derived)	PROMIS Pain Behavior t-score	IF PAINBEH = 8, 20.0 IF PAINBEH = 9, 28.4 IF PAINBEH = 10, 30.7 IF PAINBEH = 11, 32.6 IF PAINBEH = 12, 34.2 IF PAINBEH = 13, 35.7 IF PAINBEH = 14, 37.1 IF PAINBEH = 15, 38.5 IF PAINBEH = 16, 39.8 IF PAINBEH = 17, 40.9 IF PAINBEH = 18, 41.9 IF PAINBEH = 19, 42.9 IF PAINBEH = 20, 43.9 IF PAINBEH = 21, 44.8 IF PAINBEH = 22, 45.7 IF PAINBEH = 22, 45.7 IF PAINBEH = 24, 47.3 IF PAINBEH = 25, 48.1 IF PAINBEH = 26, 48.8 IF PAINBEH = 27, 49.6 IF PAINBEH = 29, 51.0

Variable	Descriptor	Derivation (if applicable)
		IF PAINBEH = 30, 51.8 IF PAINBEH = 31, 52.5 IF PAINBEH = 32, 53.2 IF PAINBEH = 33, 53.9 IF PAINBEH = 34, 54.7 IF PAINBEH = 35, 55.4 IF PAINBEH = 36, 56.2 IF PAINBEH = 37, 57.0 IF PAINBEH = 38, 57.7 IF PAINBEH = 40, 59.4 IF PAINBEH = 41,60.3 IF PAINBEH = 42, 61.2 IF PAINBEH = 43, 62.2 IF PAINBEH = 44, 63.3 IF PAINBEH = 45, 64.6 IF PAINBEH = 46, 66.2 IF PAINBEH = 47, 67.9 IF PAINBEH = 48, 80.0
WPITOT (derived)	Widespread Pain Index	∑(PSAQSHLDRT, PSAQSHLDLT, PSAQUARMRT, PSAQUARMLT, PSAQLARMRT, PSAQLARMLT, PSAQHIPRT, PSAQHIPLT, PSAQULEGRT, PSAQULEGLT, PSAQLLEGRT, PSAQLLEGLT, PSAQJAWRT, PSAQJAWLT, PSAQCHEST, PSAQUBACK, PSAQLBACK, PSAQNECK)
CARDSX (derived)	Cardinal Symptoms of JFM	Σ(PSAQFATIGUE_STD, PSAQTIRED_STD, PSAQMEMORY_STD)
SSCHK (derived)	Somatic Symptoms Total	∑(PSAQWEAKNESS,PSAQNERVO US,PSAQEYES, PSAQNUMB, PSAQDEPRESS, PSAQITCHING, PSQAMIGRAINE, PSAQURINATION, PSAQDIZZY, PSAQCRAMPS, PSAQAPPETITE, PSAQBREATH, PSAQCONSTIPATE, PSAQCONSTIPATE, PSAQVISION, PSAQTHINK,PSAQHRTBURN, PSAQEARS, PSAQMOUTH, PSAQEARS, PSAQMOUTH, PSAQNAUSEA, PSAQBRUISE, PSAQTENDER, PSAQBRUISE, PSAQINSOMNIA, PSAQSENSITIVE)

Variable	Descriptor	Derivation (if applicable)
SOMSX (derived)	Somatic Symptoms Score 0=no symptoms 1=few symptoms 2=moderate symptoms 3=great deal of symptoms	IF SSCHK = 0, SOMSX ="0", IF SSCHK GT 0 AND <= 5, SOMSX = "1", IF SSCHK >= 6 & <= 9, SOMSX ="2", IF SSCHK >=10, SOMSX ="3"
SSITOT (derived)	Symptom Score	CARDSX + SOMSX
PSAT_TOT (derived)	PSAT Total Score	Σ(WPITOT, SSITOT)
FMGROUP (derived)	Juvenile Fibromyalgia Groups 0=Non-JFM 1=JFM	IF WPITOT >=7 AND SSITOT>=5, FMGROUP = "1"; or IF WPITOT >=3 AND <= 6 AND SSITOT>=9, FMGROUP = "1"; ELSE FMGROUP = "0"
CASPETOT (derived)	COVID Impact Score	∑(CASPE1_STDCASPE16_STD)
BEIGHTON (derived)	Joint Hypermobility Score (Range: 0-9)	PERTFINGER_STD + PELTFINGER_STD + PERTELBOW_STD + PELTELBOW_STD + PERTTHUMB_STD + PELTTHUMB_STD + PERTKNEE_STD + PELTKNEE_STD + PELTKNEE_STD + PEPALMS_STD
RSOVERALL_ST D	Clinician Global Assessment Scale Range 1-10; 1=Very Poorly, 10=Very Well	
MEDGROUP	Classification of specific medication into medication class	1=antidepressants; 2=other psychotropics; 3=NSAIDS; 4=anticonvulsants; 5=musclerelaxants; 6=non-opioid analgesics
MEDGROUPYN	Participant taking any medications within medication class	1=Yes 0=No
MEDGROUPTOT	Total medications taken per medication class	
MEDTOT	Total number of medications overall	

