1.	Gait and Balance : standard gait analysis for walking gait at both self-selected and prescribed speed. (1.2 m/s) using a 10 camera, real-time, high speed, 3-D motion analysis system (Eagle, Motion Analysis Corp., Santa Rosa, CA). Lower extremity dynamic stability will be assessed using the star excursion balance test (SEBT).	X		x	X				
2.	Strength: Bilateral strength assessments will be performed with an isokinetic dynamometer (Biodex Medical Systems, Shirley, NY) for knee strength and isometric dynamometry for hip abduction strength ¹⁰	X		X	х				
V.	Fitness Assessments								
1.	Harvard Step Test: is a test of aerobic fitness in which the participant steps up and down on the platform at a rate of 30 steps per minute (every two seconds) for 5 minutes or until exhaustion.	X		x	x	х			
2.	6-minute Walk Test: the distance an individual is able to walk over a total of six minutes on a hard, flat surface. Has been frequently used as a measure of fitness in fibromyalgia research.	X		Х	Х	Х			
Seco	ndary Measures								

1.	Daily Diary Report: Patients will record daily diaries of pain, fatigue, sleep quality, mood, stress, muscle soreness and physical activity level ratings. All of these are measured on a 0-10 VAS scale. They will be instructed to complete these diaries electronically using a link sent to their smart-phone (or paper-pencil diaries if they do not have access to a mobile device or computer).	Durir treatr	ng activ nent	Х	х		
2.	Adherence: Adolescents with JFM will also complete daily diaries of home practice of coping skills and physical exercises to measure self-reported adherence using items which will be built into the smartphone application or paper diary. During follow-up , a retrospective self-report checklist of continued practice of coping skills/exercise will be completed.	Durir treatr	ng activ nent	Х	х		
3.	Pain Catastrophizing Questionnaire: 13 -item measure used to assess extent of catastrophic thinking about pain in children and adolescents	Х		Х	Х		
4.	Pain Coping Efficacy: Three item subscale from the Pain Coping Questionnaire (PCQ) that assesses perceived ability to manage and cope with pain ¹¹¹¹¹¹	Х		Х	Х	Х	

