## 6.1 Descriptive Statistics

Data analysis will begin with a review of all relevant variables in the dataset. For continuous variables, parametric measures of central tendency, variability, and association, will be computed. Distributional properties of potential outcomes will be evaluated and robust estimation techniques (MLR estimation, bootstrap resampling) will be used to guard against Type-1 errors that typically result from non-normal response variable data.

**Descriptive statistics.** Descriptive statistics (mean, median, std, min, max) will be computed for the following variables at each determined assessment time point: (with baseline only baseline only for demographics): e.g., AGE, INCOME, MEDTOT, CGA, PRFAVGPN\_RAW, FDITOT, CDITOT, PCSTOT, PCQTOT, TSKTOT, FATIG,

PAINBEH, PAININT, WPITOT, CARDSX, SSITOT, SOMSX, SSCHK, CASPETOT, BEIGHTON

**Frequency Counts/Percentages.** Frequency counts and percentages will be computed for the following variables: GROUP, FORMAT, SEX, RACE, ETHNIC, INCOME, INSURANCE, CRGVR1, EDU1, CRGVR2, EDU2, ENGRGRD, FMGROUP

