## 6.2 Baseline Comparisons

Baseline group comparisons will be used to test for equivalence among the three intervention groups at baseline (Samples 1, 2, 3 by GROUP)

- One-way ANOVA/Kruskall Wallis: AGE, INCOME, RSOVERALL, FDITOT, APVAS, FDITOT, CDITOT, PCSTOT, PCQTOT, TSKTOT, FATIG, PAINBEH, INTERF, WPITOT, CARDSX, SSITOT, SOMSX, SSCHK, CASPETOT, BEIGHTON
- Chi-square/Exact Test: FORMAT, SEX, RACE, ETHNIC, INCOME, INSURANCE, CRGVR1, EDU1, CRGVR2, EDU2, ENGRGRD, FMGROUP

Specific tests used will depend on distributional properties and expected cell counts. Test results with p-values <.10 will be considered as candidates for inclusion in the multiple covariate models in the analyses below.

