# 6.5 Exploratory Analyses

Mechanistic models of how treatment-related improvements in psychological (coping, fear of movement, adherence) and physical factors (objectively measured physical activity, biomechanical changes and fitness) explain changes in disability and pain outcomes across the three groups will be examined on an **exploratory basis**. Multiple path mediation analyses. 1) Selected indirect pathways between psychological coping skills, decreased fear of activity, and improved biomechanics (predictors), physical activity engagement and physical fitness (mediators), and functional disability and pain intensity (outcomes) will be tested for statistical significance within each of the three (FIT, CBT & GAE) groups, and 2) The magnitudes of the indirect effects will be tested for statistically significant differences between the three treatment groups. The False Discovery Rate will be used to maintain the nominal Type-1 error rate for all indirect effect tests.

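### As written, the SAP reverse-codes PCQDEAL_STD but sums PCQDEAL, a name it never defines, so the stated reversal does not enter the three-item coping score PCQTOT

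*SAP*

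**What the plan says.** The protocol (section 4, Study Assessments) describes the coping measure as a "Three item subscale from the Pain Coping Questionnaire (PCQ) that assesses perceived ability to manage and cope with pain". The SAP scores it in two lines under Other Variables T1, T3-T7. The first is "RECODE PCQDEAL_STD (1=5) (2=4) (3=3) (4=2) (5=1) EXECUTE". It names no new target variable, so the reversed values overwrite PCQDEAL_STD. The second is "COMPUTE PCQTOT = PCQCHANGE_STD + PCQDEAL + PCQMOOD_STD". The first and third terms carry the _STD suffix and the middle one does not.

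PCQTOT is then used as follows:

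- SAP 6.1 lists it among the variables to be described at the assessment time points ("FDITOT, CDITOT, PCSTOT, PCQTOT, TSKTOT, FATIG").
- SAP 6.2 includes it in the baseline comparisons, with the rule "Test results with p-values <.10 will be considered as candidates for inclusion in the multiple covariate models in the analyses below".
- Tables 3 and 4 have a Pain Coping row for each arm.
- SAP 6.5 plans mediation models with "Selected indirect pathways between psychological coping skills, decreased fear of activity, and improved biomechanics (predictors". It does not name PCQTOT, but PCQTOT is the only derived total labelled as coping.

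**The concern.** A reversal has an effect only if the reversed variable is the one that is summed. Here the two names differ, and the summed name has no definition, so an analyst cannot tell from the SAP what the middle term contains. With only three items, one item keyed the wrong way is a third of the score and works against the other two. A real gain in coping would then partly cancel within the total. Differences between FIT Teens and the two comparators on coping would shrink, as would any mediation path through coping. A mis-keyed baseline score could also change whether coping is put forward as a covariate.

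**Working it through.** The SAP gives no figure that depends on this score, so there is nothing to reproduce. The check is a reading of the two lines, followed by the consequence of each possible meaning of PCQDEAL.

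**Step 1: compare with the SAP's own practice.** In the same table, the depression score (CDITOT) is also built by reversing some items in place. Its sum then uses the same _STD names that were recoded, so the reversal enters the total. The coping score recodes one name and sums another. PCQDEAL occurs only in the sum.

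**Step 2: list what PCQDEAL could be.**

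| Case | PCQDEAL is | Item reverse-keyed? | Result |
|---|---|---|---|
| a | not in the dataset | either | the line fails and no score is produced |
| b | the un-reversed 1-5 response | yes | the total is mis-keyed |
| c | the un-reversed 1-5 response | no | the total is right and the recode has no effect on it |
| d | a typing slip for PCQDEAL_STD | yes | right once the name is corrected |

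**Step 3: size of the error in case b, per patient.** For a response x on the 1-5 code, the reversed value is 6 − x. Using x instead changes the total by x − (6 − x) = 2x − 6, which is −4, −2, 0, +2 or +4 points for x = 1 to 5. Assume that all three items run 1-5. Take three consistent patients with responses (CHANGE, DEAL, MOOD) of (1, 5, 1), (3, 3, 3) and (5, 1, 5):

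- Intended totals: 1+1+1 = 3, 3+3+3 = 9, 5+5+5 = 15.
- Totals as written: 1+5+1 = 7, 3+3+3 = 9, 5+1+5 = 11.

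The distance between the lowest and highest patient falls from 12 to 4 points, which is one third.

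**Step 4: size of the error in case b, for a group comparison.** Assume that, once correctly keyed, the items a, b and c (c being DEAL) have unit variance, a common correlation r and the same shift δ.

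- Correct total a + b + c: variance 3 + 6r, shift 3δ.
- Total as written, a + b − c plus a constant: variance 3 − 2r, shift δ.
- Covariance of the two: (2 + 2r) − 1 = 1 + 2r.
- Correlation: (1 + 2r) / √[(3 + 6r)(3 − 2r)].
- Ratio of standardised effects: [δ/√(3 − 2r)] / [3δ/√(3 + 6r)] = √(3 + 6r) / [3√(3 − 2r)], which is algebraically the same quantity.

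| r (assumed) | Calculation | Correlation with correct total, and share of standardised effect kept |
|---|---|---|
| 0.3 | 1.6 / √(4.8 × 2.4) | 0.47 |
| 0.5 | 2.0 / √(6.0 × 2.0) | 0.58 |
| 0.7 | 2.4 / √(7.2 × 1.6) | 0.71 |

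The share of the change in points that remains is δ/3δ = one third, whatever r is.

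**The case against.** The strongest reply is that this is a slip of notation with no effect on results. Four parts of it deserve an answer.

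**Lost text.** The recode line lacks the full stop that closes the corresponding line for the depression score, and other parts of the table are visibly damaged in conversion. A clause creating PCQDEAL may have dropped out. This cannot be excluded, but nothing shows it. The coping lines are legible, and both neighbouring terms in the sum keep their suffix.

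**Item direction.** The documents do not give the response anchors. If the item is not reverse-keyed and PCQDEAL is the original response, the sum as written is correct and the recode line is the superfluous one. This stands. A reader might infer that the coping outcome is certainly wrong, or that coping effects will be roughly halved. The documents do not support that, because they show neither the content of PCQDEAL, nor the item's keying, nor the program that was run.

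**Reach.** A reader might also infer that the trial's main conclusions are at risk. They are not scored from this variable. The primary aims use functional disability, the secondary aim uses pain, and no hypothesis in SAP 6.3 or 6.4 compares coping between arms. The only route to those models is the covariate screen, which merely nominates candidates.

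**Fear of movement.** TSKTOT includes one item without the suffix ("TSKNORMAL,TSKPAIN_STD"), the only one of its 11. It is tempting to call this the same error. No item of that scale is recoded, so no reversal is lost and no bias is shown. Other totals in the table, such as WPITOT and SSCHK, also sum names without the suffix. It is a name to check and no more.

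**Conclusion.** The concern holds for the written specification. The reversed variable and the summed variable have different names, the summed one is undefined, and read literally the reversal does not enter PCQTOT. That is a wrong derivation rule, whatever the analysis program does.

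The consequence is conditional. Only if PCQDEAL exists as an un-reversed 1-5 response and the item is truly reverse-keyed is the score mis-keyed. The loss is then two thirds of the change in points. The standardised effect falls to about 47% to 71% of its correct size for inter-item correlations of 0.3 to 0.7, assuming equal variances and equal shifts. In the other cases the line fails visibly, or the total is right and only the text needs correcting. It is worth correcting because coping is a reported outcome row and the probable coping variable in the mediation models.

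**What to change.** 1. Confirm from the case report form which of the three items, if any, runs in the opposite direction, and state the item range and the direction of the total in the SAP.
2. If PCQDEAL is the reversed item, sum the recoded variable under one name: PCQTOT as PCQCHANGE_STD plus PCQDEAL_STD plus PCQMOOD_STD. Alternatively, recode into a new variable and sum that. The second form is safer, because an in-place recode run twice on saved data undoes itself.
3. If no reversal is needed, delete the recode and sum the un-recoded coded item.
4. Check the executed program against the corrected lines, and rerun the coping results if they differ.
5. Check the variable name TSKNORMAL in TSKTOT at the same time.

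The cost is one or two lines in the derivation table and a program check. No new data are needed.
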